Information about study subjects will be kept confidential and managed according to the requirements of the Health Insurance Portability and Accountability Act of 1996 (HIPAA). Source documents are maintained in PennChart. No source documents will be printed or maintained in paper form at the study site. Data from PennChart will be recorded in Penn Medicine's REDCap system. The investigator and study team will have access to PHI within PennChart and REDCap. We will label all PHI within REDCap as identifiable information so that de-identified exports are possible. All reports that include identifiable information will be stored on the Innovation Center secure drive, maintained behind the UPHS firewall. Direct identifiers will be maintained on RedCap until manuscript publication in case additional chart review is needed for confirmation of results. Once data analysis and manuscripts have been published, direct identifiers will be deleted from RedCap and the de-identified database will be stored on the Innovation Center secure drive.

Objectives

Overall objectives

In addition to providing direct outreach to patients in included practices, we have the following aims:

Aim 1: To evaluate if a differentiated box increases uptake of mailed FIT

Aim 2: To evaluate if text messaging could increase uptake for mailed FIT

Aim 3: To evaluate if sending personalized reminders increases uptake

Primary outcome variable(s)

The primary outcome will be the percentage of patients who complete FIT within 4 months of outreach.

Secondary outcome variable(s)

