Secondary outcomes will be completion of FIT within 6 months, and completion of any CRC screening within 4 and 6 months. We will also track what percentage of the completed FIT that have positive results and schedule and complete colonoscopy, as well as the results of the procedure (adenoma, advanced adenoma, cancer). We will compare response rates by age, race/ethnicity, insurance, income (by zip code), MyPennMedicine status, and completion of prior CRC screening. We will also compare colorectal cancer screening completion of the patients in the trial to patients in similar practices that were not included in the trial to understand the effect size for outreach compared to no outreach. We will use the same inclusion and exclusion criteria to identify a cohort of patients in the control practices, and compare completion of any colorectal cancer screening method to the trial participants during the trial follow-up period.

Background

The initial and subsequent surges from the COVID-19 pandemic caused many patients to delay evidence-based colorectal cancer (CRC) screening. A major challenge was that many of our CRC screening efforts relied on screening colonoscopy. Many patients deferred screening, and there were also access issues related to scheduling and clinician capacity.

In September 2020, Penn Medicine identified CRC screening among Black patients as a system-wide goal. Due to issues with endoscopy capacity and limited scope of clinic-based outreach efforts, the Colorectal Cancer Strategy group conducted a sprint in the Spring of 2021 to send mailed fecal immunochemical test (FIT) kits directly to patients based on prior experiences from pilot projects. We sent out approximately 4000 kits to practices with a high proportion of minority patients, and included a user-friendly Penn Medicine-branded box as well as text message navigation, resulting a 25% response rate.

Due to continued endoscopy capacity issues, we would like to conduct a similar outreach campaign, but also rigorously evaluate the effectiveness of the designed box, text messaging, as well as a reminder that might increase uptake. These behavioral interventions require additional resources, so the goal is to determine effectiveness of each approach, which will inform future efforts.

Study Design

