We estimate an 18% response rate in the simple outreach arm (no box, no text message, no reminder), based on a prior outreach and findings from other outreach activities. We anticipate an additive effect from each intervention with an effect size of 4 percentage points for each enhancement, based on prior work and other studies. For the box mailing comparison, we therefore anticipate an aggregate response rate of 22% in the no box arm (with half the patients receiving text messaging and half receiving reminders in a factorial design). See Figure 1. An equal allocation of 2,500 in each arm will provide over 90% power to detect a 4 percentage point increase in response rate in the box order arm using the chi-squared test of proportions and intention-to-treat protocol, and considering a two-sided P value less than 0.05 as statistically significant [STATA: power twoprop .22 .26, n(5000) a(.05)]. This increase is clinically meaningful and would justify investment by a health system in the materials and packaging of the box after it is implemented.

[figure not shown]
We estimate a 22% response rate in the no text messaging arm, based on prior work. Similar to the box comparison, half the patients will receive the box and half will be assigned to receive a reminder in a factorial design. The eligible population of 5,000 would provide over 90% power to detect an increase in response rate of 4 percentage points in the text message arm compared to no text message [STATA: power twoprop .22 .26, n(5000) a(.05)]. This increase would justify investment in the text messaging technology and implementation.

For the personalized mailed reminder comparison, we estimate a 22% response rate in the no reminder arm that includes 2,500 patients. This will provide over 90% power to detect an increase in response rate of 4 percentage points in the personalized mailed reminder arm compared to no mailed reminder. [STATA: power twoprop .22 .26, n(5000) a(.05)]. This increase would justify investment in the resources to mail reminder letters.

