For the main comparisons, we will use the chi-squared test of proportions to calculate difference and 95% confidence intervals, along with P-value. We will also conduct analyses for the secondary outcomes of FIT completion at 6 months, and any CRC screening at 4 and 6 months. We will also compare colorectal cancer screening completion of the patients in the trial to patients in similar practices that were not included in the trial to understand the effect size for outreach compared to no outreach. We will use the same inclusion and exclusion criteria to identify a cohort of patients in the control practices, and compare completion of any colorectal cancer screening method to the trial participants during the trial follow-up period.

For the exploratory subgroup analyses, we will fit multivariable logistic models with treatment group, sex, age, race, ethnicity, household median income, patient portal status, and one treatment by covariate interaction at a time. We will conduct likelihood ratio tests to examine significance of the interaction term in each model. We will report the estimated log odds ratio along with a 95% confidence interval for each interaction, which quantifies the differential effect of treatment between subgroups (relative to a reference group for categorical covariates), adjusting for all other covariates in the model. We will report p-values both unadjusted and adjusted for multiple comparisons using the Holm procedure.

Figure 1

Data Confidentiality

Paper-based records will be kept in a secure location and only be accessible to personnel involved in the study. Computer-based files will only be made available to personnel involved in the study through the use of access privileges and passwords. Wherever feasible, identifiers will be removed from study-related information.

Subject Confidentiality

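### The three main comparisons use no baseline covariates; prespecified adjustment would probably buy a small gain in precision at almost no cost

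*Combined protocol and SAP*

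**What the plan says.** The confirmatory analysis is one sentence in the Analysis Plan: "For the main comparisons, we will use the chi-squared test of proportions to calculate difference and 95% confidence intervals, along with P-value". No covariate is named, and practice, the stratification factor, is not mentioned either. The outcome is binary: "The primary outcome will be the percentage of patients who complete FIT within 4 months of outreach". The power statements in the same section rest on the same unadjusted test.

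Baseline variables appear in two other places.

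- Secondary outcome variable(s): "We will compare response rates by age, race/ethnicity, insurance, income (by zip code), MyPennMedicine status, and completion of prior CRC screening".
- Exploratory subgroup analyses, Analysis Plan: "we will fit multivariable logistic models with treatment group, sex, age, race, ethnicity, household median income, patient portal status", with one treatment-by-covariate interaction at a time. Insurance and prior CRC screening are not in this list; sex is in this list but not in the other.

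Under Procedures, the electronic extract that identifies patients is said to include contact details and demographics.

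**The concern.** The plan intends to hold and model these variables, but leaves them out of the three comparisons on which the investment decisions rest. If any of them predicts FIT return, chance imbalance between arms remains as noise in the estimated effects, and the variation they explain stays in the standard error. A test stratified by practice would not remove the patient-level part.

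Two features make even a modest gain worth having. The sample is fixed at about 5,000 by laboratory capacity (Accrual), so precision cannot easily be bought with more patients. And there are three aims, each with its own threshold of 4 percentage points. A covariate-adjusted risk difference keeps the intention-to-treat comparison and the percentage-point scale in which those thresholds are set.

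**Working it through.** **Inputs from the Analysis Plan.** Rate without the factor: "we therefore anticipate an aggregate response rate of 22% in the no box arm", with the same 22% used for text and letter. Effect: "We anticipate an additive effect from each intervention with an effect size of 4 percentage points for each enhancement". Size and stated power: "An equal allocation of 2,500 in each arm will provide over 90% power to detect a 4 percentage point increase in response rate". Significance level: "considering a two-sided P value less than 0.05 as statistically significant".

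**Step 1: reproduce the stated power.** With n = 2,500 per arm and a mean rate of 0.24:

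- SE under the null = √(2 × 0.24 × 0.76 / 2,500) = 0.01208
- SE under the alternative = √((0.22 × 0.78 + 0.26 × 0.74) / 2,500) = √(0.364 / 2,500) = 0.01207
- Power = Φ((0.04 − 1.96 × 0.01208) / 0.01207) = Φ(1.353) = 91.2%
- 95% CI half-width = 1.96 × 0.01207 = 0.02365, or 2.36 points

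With a continuity correction the power is 90.7%. The plan's figure stands.

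**Step 2: effect of adjustment.** Let R² be the share of outcome variance explained by the baseline covariates. In large samples, adjustment multiplies the variance of the risk difference by (1 − R²), so both standard errors are multiplied by f = √(1 − R²). The equivalent unadjusted sample is 5,000 / (1 − R²). R² is not in the documents; the values below are assumptions.

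| Assumed R² | f | Half-width (points) | Power | Equivalent patients |
|---|---|---|---|---|
| 0 | 1.000 | 2.365 | 91.2% | 5,000 |
| 1% | 0.995 | 2.353 | 91.5% | 5,051 |
| 2.5% | 0.987 | 2.335 | 91.9% | 5,128 |
| 5% | 0.975 | 2.305 | 92.5% | 5,263 |
| 7.5% | 0.962 | 2.275 | 93.1% | 5,405 |

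**Step 3: what such R² values mean.** For a binary predictor with prevalence q and a difference d in response, R² = q(1 − q)d² / (0.24 × 0.76).

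- One 50/50 predictor with d = 10 points: 0.25 × 0.01 / 0.1824 = 1.4%. With d = 20 points: 5.5%.
- Two independent 50/50 predictors with d = 12 and 6 points: 0.25 × (0.0144 + 0.0036) / 0.1824 = 2.5%. With 20 and 12 points: 7.5%.
- The 12- and 6-point pair with 80/20 splits: 0.16 × 0.018 / 0.1824 = 1.6%.

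**Step 4: check by simulation.** Trials of 5,000 patients were simulated and analysed by logistic regression standardised to a risk difference.

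- In 600 trials per setting, the ratio of adjusted to unadjusted standard error was 1.00 at R² = 0, 0.99 at about 1.5% and 0.98 at about 6% (formula: 0.97). The mean estimate was essentially unchanged.
- In a separate set of 6,000 trials, the ratio was 0.985 at R² 2.5% and 0.960 at 7.5%. Simulated power rose from 90.8% to 91.4% and from 90.9% to 93.3%.

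**Step 5: all three factors together.** Treating the three tests as roughly independent, the chance of detecting all three 4-point effects is 0.912³ = 76% unadjusted, 0.925³ = 79% at R² 5% and 0.931³ = 81% at R² 7.5%.

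**The case against.** The strongest reply is that nothing needs repair. The unadjusted comparison is valid under randomisation, matches the test used for power, exceeds 90% power, and suits a pragmatic trial that reports absolute differences to operational decision-makers. The gain is at most 2.365 − 2.275 = 0.09 points of half-width over the assumed range, which is unlikely to change an adoption decision. All of this stands, and it is why the point is one of efficiency only.

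The assumed R² may also be generous. A 50/50 split maximises R² for a given difference, and adding two R² values assumes independent predictors. Eligibility removes patients who are up to date or have a polyp history, which leaves the prior-screening split unknown. Excluding uninsured and self-pay patients narrows the insurance variable. This also stands, and it is why the range starts at 1% and zero gain is kept open.

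Three stronger readings are tempting, and the documents do not support them.

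- That every primary interval is certainly too wide. This needs covariates that predict response, and no prognostic strength is given.
- That the plan expects response to differ by these variables, or regards them as strong predictors. It says only that response will be compared across them.
- That all of them are stated to be in the pre-randomisation extract. Only demographics are explicit. Screening history and insurance status must be read at least in part to apply the eligibility criteria; portal status appears only in the planned analyses.

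**Conclusion.** The point holds as a low-cost efficiency recommendation. The primary analysis leaves out baseline variables that the trial plans to hold. Under an assumed R² of 1% to 7.5%, using them would narrow the primary intervals by about 0.5% to 4% and add about 0.3 to 1.9 percentage points of power per comparison. The true figure cannot be sized from the documents and is nil if none of the variables predicts FIT return. With 5,000 patients and a short covariate list, no meaningful loss of precision is expected. A reader should not infer that the chi-squared analysis is biased or that the trial is underpowered: neither is so.

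**What to change.** In the Analysis Plan, replace the sentence on the main comparisons as follows.

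- **Primary estimate for each factor:** a standardised risk difference with a robust 95% CI and P value, from a logistic model with box, text and letter indicators, practice, age, sex, race, ethnicity, insurance, zip-code income, portal status and prior CRC screening.
- **Covariates:** all taken as of before randomisation, with an unknown category for missing values. Insurance and prior CRC screening are additions to the list now given for the exploratory models. Practice belongs in the model because randomisation is stratified by it.
- **Supporting analysis:** the unadjusted chi-squared comparison already planned.
- **Secondary outcomes:** the same model for FIT completion at 6 months and any CRC screening at 4 and 6 months.

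The choice should be fixed before outcomes are seen, since adjustment chosen afterwards is open to challenge. The cost is a paragraph of wording, some programming, confirmation that the extract holds insurance, portal status and prior screening at baseline, and a slightly less simple primary analysis. It needs no extra patients.
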